12.3 Additional analyses

Additional analyses are performed on PD and tentative disease specific marker variables and pharmacoeconomic variables.

12.3.1 Pharmacodynamics and tentative disease specific marker analysis

PD and tentative disease specific marker variables to be analysed are MxA concentration in whole blood samples from baseline up to D13, CD73 concentration in serum samples from baseline up to D6 and potential Inflammatory Markers (e.g. IL-6 and HIF-1 α) in serum samples from baseline up to D13.

These will be summarised using descriptive statistics and analysed using Repeated measurements ANOVA model with main effects of treatment and day and their interaction. Correlations between the repeated observations will be modelled using compound symmetry covariance structure. The model will be used to estimate population geometric means (95 % CI) for the treatment groups by timepoint.

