- Length of ICU stay, in terms of ICU free days at D30
- Length of hospital stay, in terms of hospital free days at D90
- Length of stay at another health care facility at D90
- Length of hemodialysis needed
- Ventilation free days at D30

3.2.4 **Exploratory endpoints assessments**

Pharmacodynamics (PD):

- MxA (protein) concentration in whole blood samples from baseline up to D13.

Tentative Disease Specific Marker:

- CD73 concentration/activity in serum samples from baseline up to D13
- Potential Inflammatory Markers IL-6 and HGF in serum samples from baseline up to D13

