6.6 Exploratory Variables

6.6.1 *Methods and Timing for Assessing, Recording and Analysing Pharmacodynamic Parameters*

Blood samples for the NAb assessments are collected at D0 pre-dose (baseline) and at D30. Blood samples for the MxA, Tentative Disease Specific Marker (CD73) and Potential Inflammatory Markers (IL-6 and HGF) assessments are collected at D0 pre-dose (baseline), at D1, D2, D3, D4, D5, D6, D9 and D13 assuming the patient is hospitalized as detailed in the study flow charts in Tables 5 and 6.

MxA, CD73, NAb and PIM blood sample preparation and sample storage details are provided in the study specific Laboratory Manual. It is essential that the actual time and date of collection of each PD sample be recorded in the sample collection form provided with the laboratory kits.

MxA, CD73 and NAb samples are analysed centrally by [REDACTED], and PIMs in [REDACTED].

The total volume of blood required for samples per patient is shown below in Table 4.

Table 4 Total Volume of Blood required for MxA, CD73 and PIMs

PD Parameter	Number of Samples	Per Sample Volume (mL)	Total Volume (mL)
CD73	9	2.5	22.5
MxA	9	2	18
PIM	9	2.5	22.5
NAb	2	2.5	5

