9.6 Examination of subgroups

Data for the primary efficacy endpoint will also be presented for key, pre-defined subgroups of patients. Concomitant use of glucocorticoids will be one key subgroup as earlier studies have suggested that it may have effect on the study treatment. As CD73 response (and IL-6 and HIF-1 α) may be also genetically determined/individual, another key subgroups will be CD73 responder status (determined by a 2-fold elevation in CD 73 (from baseline to peak value)). In addition, if analyses indicate yet another, but currently unknown but relevant subgroups, they will be analysed as separate subgroup analyses for exploratory purposes

Key subgroups included in analyses

- Concomitant use of glucocorticoids
- CD 73 responder status (responders vs. non-responders)
- IL-6 responder status
- HIF-1 α responder status

10 Demographic and other baseline characteristics

Number of patients enrolled into the study at screening and the reasons for screening failures will be summarized. The number of patients entering and completing the study will be summarized. All patients discontinuing the study will be summarized together with the reason(s) for discontinuation.

Demographic and baseline characteristics will be summarized by treatment using descriptive statistics. Following variables will be analysed.

- Gender
- Age at entry
- Race
- Height
- Weight
 - If actual weight is not available for a patient, then predicted body weight will be used in its place
 - Predicted body weight (kg) is calculated using the following formulae:
 - Males: $50 + 0.91(\text{height in cm} - 152.4)$
 - Females: $45.5 + 0.91(\text{height in cm} - 152.4)$
- Major surgical outcomes affecting patient
 - Open abdomen (yes/no)
 - Left renal vein ligated (yes/no)
 - Clamping time above the renal arteries
- Medical history
- Concomitant medications/therapies
- Pregnancy test (females of child bearing potential).

Similarly, the duration of the surgical procedure and peri procedural information will be summarized by treatment. Additional concomitant procedures will be listed only.

Medical history and concomitant medications/therapies will be presented only by frequency and subject count-based tables according to WHO Anatomical Therapeutic Chemical (ATC) classification.

Pregnancy test results (females of child-bearing potential) will be presented only descriptively by a subject count-based table.

11 Extent of exposure and compliance

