13.3 Other safety variables

Other safety variable to be analysed are vital signs (body temperature, blood pressure, heart rate) and physical examination.

Vital signs data is summarized by treatment groups separately at D0, D1, D2, D3, D4, D5, D6, D9, D13 and D30. Absolute values and changes from baseline are both summarized. In addition, the maximum change from baseline over the 30-day follow-up period will be calculated for each patient and summarized. Vital signs summaries will be in terms of mean, median, SD, minimum and maximum.

Physical examination covering all the major organ systems will be performed at screening and D30. These will be summarized by treatment groups and visits using frequency and percentage of normal/abnormal observations. In addition, shift tables will be provided describing the change from screening to D30.

14 Completion and premature discontinuation

Completion and premature discontinuation will be listed. The reasons for premature discontinuation will be presented.

15 Deviations from the analyses planned in the study protocol

Study was discontinued after the first Interim analysis. Due to the early discontinuation, the planned O'Brien and Fleming correction will not be applied to the primary analysis. Instead, the standard p-value of less than 0.05 will be considered statistically significant.

Due to low number of accrued patients, the center effect was not further explored in the analyses. Analysis of study centers was limited to summary statistics for baseline information.

Due to the early discontinuation of the study, the pharmacoeconomic endpoints (see section 12.3.2) will not be analysed.

There are no other major deviations in the statistical analysis plan from the analyses planned in the study protocol.

16 Execution of statistical analyses

Statistical analyses will be performed by [REDACTED].

17 Hardware and software

[figure not shown]
Statistical analysis, tables and patient data listings will be performed with SAS[®] version 9.4 or later for Windows (SAS Institute Inc., Cary, NC, USA).

18 References

Clinical Study Protocol (FP1CLO006), Final Protocol version 05 (16 April 2019), Faron Pharmaceuticals Ltd.

19 Appendices

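### The SAP stops the exploratory CD73 analysis at D6 although the protocol runs it to D13, is inconsistent about the inflammatory markers, and records neither point in section 15

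*SAP*

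**What the plan says.** **CD73 in the protocol.** Section 3.2.4 lists, among the exploratory endpoints, "CD73 concentration/activity in serum samples from baseline up to D13". Section 6.6.1 says that the MxA, CD73 and inflammatory-marker samples "are collected at D0 pre-dose (baseline), at D1, D2, D3, D4, D5, D6, D9 and D13 assuming the patient is hospitalized". The CD73 row of Table 4 (samples, mL per sample, total mL) reads "CD73 9 2.5 22.5".

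**CD73 in the SAP.** Sections 5 and 12.3.1 both limit the analysis to "CD73 concentration in serum samples from baseline up to D6". In both places MxA and the inflammatory markers keep D13. The follow-up flow chart in SAP 19.2 still schedules CD73 on D9 and D13.

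**Inflammatory markers.** Protocol 3.2.4 has "Potential Inflammatory Markers IL-6 and HGF in serum samples from baseline up to D13", and the list of study personnel gives a central laboratory for HGF and IL-6. SAP sections 3 and 5 also name IL-6 and HGF. SAP 12.3.1 instead has "potential Inflammatory Markers (e.g. IL-6 and HIF-1" followed by the letter alpha, and SAP 9.6 lists HIF-1 alpha responder status as a key subgroup.

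**Responder subgroup.** SAP 9.6 defines "CD73 responder status (determined by a 2-fold elevation in CD 73 (from baseline to peak value" and states no window for the peak.

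**Declared deviations.** SAP section 15 covers the significance level, the centre effect and the pharmacoeconomic endpoints. It then says: "There are no other major deviations in the statistical analysis plan from the analyses planned in the study protocol".

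**The concern.** CD73 is the marker on which the trial's mechanism rests (protocol 1.1 and 1.3). Its timing is also the protocol's reason for excluding deaths in the first 36 hours from the efficacy set (8.5.1). Ending the analysis at D6 means that no estimate describes CD73 once dosing has been over for more than about a day, so the plan cannot show whether a rise persists or fades.

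The unstated peak window affects a key subgroup for D30 mortality: whether D9 and D13 count could change who is a responder. The conflicting marker names leave open which inflammatory markers will be modelled.

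SAP section 2 places this version after the interim analysis and the decision to discontinue. It also says that the preceding SAP concentrated on the primary analyses. The available documents therefore do not show that the D6 limit or the HIF-1 alpha entries were fixed beforehand, and a reader would look to section 15 for an explanation.

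**Working it through.** **1. Reproduce the plan's own count.** Protocol 6.6.1 gives sampling days D0, D1, D2, D3, D4, D5, D6, D9 and D13, which is 9 time points. At 2.5 mL each, 9 × 2.5 = 22.5 mL. This matches Table 4, so the protocol is consistent in planning nine CD73 samples.

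**2. Count under the SAP window.** Baseline to D6 is D0 to D6, or 7 time points, of which 6 are after baseline. The number left out is 9 − 7 = 2 (D9 and D13).
- Share of all scheduled time points: 2/9 = 22%.
- Share of post-baseline time points: 2/8 = 25%.

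These are maxima per patient. Protocol 6.6.1 and the notes to Tables 5 and 6 limit these samples to patients still in the hospital where they were operated on.

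**3. What the two time points add.** Dose 6 falls on D5, and the D6 sample is due 22 ± 2 hours after it (protocol Table 6 and 7.5.2). D9 is about 9 − 5 = 4 days after the last dose, and D13 about 13 − 5 = 8 days after. For a patient who receives all six doses, every other post-baseline sample is taken within about a day of a dose.

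**4. Effect on responder status.** The peak over D1–D13 cannot be lower than the peak over D1–D6. Extending the window can therefore only move a patient from non-responder to responder. A patient whose CD73 first doubles on D9 would be a non-responder with a D6 window and a responder with a D13 window. How many such patients there are cannot be known from the documents.

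**5. Marker names side by side.**

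| Place | Inflammatory markers named |
|---|---|
| Protocol 2.2 and 3.2.4 | IL-6, HGF |
| SAP 3 and 5 | IL-6, HGF |
| SAP 9.6 (responder subgroups) | IL-6, HIF-1 alpha |
| SAP 12.3.1 (analysis) | IL-6, HIF-1 alpha, given as examples |
| SAP 19.3 (PIM tables and ANOVA) | none by name |

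The protocol does not name HIF-1 alpha as a study marker; the term occurs only in the title of a cited paper.

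**6. Check against section 15.** None of its three declared items concerns CD73, its activity measure, or the marker list.

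**The case against.** Four points can fairly be made for the plan, and each limits what may be concluded.

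- **Section 15 may not be false.** It denies other *major* deviations only. The protocol files CD73 under exploratory endpoints, and an author could call a shorter exploratory window minor. This stands, but section 15 does declare the centre effect and the pharmacoeconomic endpoints, so it is incomplete by its own practice. The protocol's slash between concentration and activity might also allow either measure; the SAP should say which was measured.
- **HGF may still be analysed.** A reader might infer from 12.3.1 that HGF has lost its analysis. The text does not support that: section 5 lists HGF among the variables to be evaluated, 12.3.1 gives its markers only as examples, and the planned marker tables are generic. What stands is a contradiction within the SAP.
- **No data are thrown away.** SAP section 9 has all collected data listed by subject, and Listings 16.2.19 and 16.2.20 cover CD73 concentration and the inflammatory markers. Only the D9 and D13 CD73 summaries and model estimates are missing. Nor can HIF-1 alpha be called uncollected: the Laboratory Manual is not available and stored serum could have been assayed. It is simply not named in the protocol.
- **Timing does not prove knowledge.** A reader might infer that the window was cut after unblinding. Protocol 5.4 does plan to open the code for the interim analysis. However, nothing says that the SAP's authors saw unblinded or marker data, SAP section 8 places database lock still ahead, and the SAP of 17.6.2019 is not available. The supported wording is *after the interim analysis*.

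**Conclusion.** The point holds as an undeclared difference between protocol and SAP on an exploratory marker, together with an internal inconsistency in the SAP. CD73 goes from concentration/activity to D13 to concentration to D6, with no reason given. At most 2 of 9 scheduled time points (22%), or 2 of 8 after baseline (25%), are left out of the summaries and model. The actual number of samples is unknown because it depends on who was still in the operating hospital. That these are the only samples more than about a day after the last dose assumes that all six doses were given; a patient who stopped early could have such a sample by D6.

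The responder peak lacks a window, and the marker names conflict between SAP 3 and 5 on one side and 9.6 and 12.3.1 on the other. The primary analysis and the sample size are unaffected, so this is a minor but worthwhile correction. The documents do not establish that data were discarded, that HGF was abandoned, or that the change was made with knowledge of treatment codes.

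**What to change.** 1. In SAP 5 and 12.3.1, analyse CD73 to D13 with the same repeated-measures model as MxA. If D9/D13 or activity data are unavailable, say so in section 15 and give the reason.
2. In SAP 9.6, state the window for the CD73 responder peak and make it the same as the analysis window.
3. In SAP 12.3.1, name HGF alongside IL-6, to agree with SAP 3 and 5 and the protocol.
4. Keep HIF-1 alpha in 9.6 and 12.3.1 only if it was assayed, and declare it in section 15 as an addition. Otherwise remove it. Do not put an HGF responder subgroup in its place, since neither document plans one.

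The cost is a few lines of SAP wording plus two time points in an existing table and model. SAP section 8 treats database lock as still to come, so the change can be made before it. No new samples or visits are needed.

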12.3.2 Pharmacoeconomic analysis

Following pharmacoeconomic endpoints were defined for the study:

- Length of ICU stay, in terms of ICU free days at D90
- Length of hospital stay, in terms of hospital free days at D90
- Length of stay at another health care facility at D90
- Length of hemodialysis needed (at D90)

Due to early discontinuation of the study, these endpoints will not be analysed.

13 Analysis of safety and tolerability

All subjects in the SAF-S analysis set (all randomised patients receiving study treatment) will be included in the safety and tolerability analysis. Safety variables to be analysed are; adverse events, clinical laboratory parameters, vital signs and physical examination.

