- All-cause mortality at D90 (3 months)
- Number of ventilator free days (VFDs) at D30
- Number of days receiving haemodialysis at D30 and D90
- Number of organ failure free days up to D30 by

	means of the SOFA score
	
• Prevalence of abdominal compartment syndrome, i.e. intra-abdominal pressure (IAP) between study groups• Neutralizing antibodies against IFN beta-1a (NAbs) in whole blood samples up to D30• Disability on D90 measured by modified ranking scale (mRS)
Safety	
• Clinically significant treatment emergent adverse events (TEAEs) up to D30 from vital signs data, laboratory data, physical examinations and spontaneous reporting when conscious
Pharmacoeconomics	
• Length of ICU stay, in terms of ICU free days at D30• Length of hospital stay, in terms of hospital free days at D90• Length of stay at another health care facility at D90• Length of haemodialysis needed• Ventilation free days at D30
Pharmacodynamics (PD)	
• MxA (protein) concentration in whole blood samples from baseline up to D13
Tentative Disease Specific Marker	
• CD73 concentration/activity in serum samples from baseline up to D13• Potential Inflammatory Markers (IL-6 and HGF) in serum samples from baseline up to D13
Design	Multicentre, randomised, double-blinded, Phase II, parallel group comparison study of the efficacy and safety of FP-1201-lyo compared to placebo in patients surviving emergency open surgery for an infra-renal ruptured abdominal aortic aneurysm. Receiving as post-surgical preventive treatment either FP-1201-lyo or placebo. Both treatment groups will receive standard supportive care.

Treatment

10µg FP-1201-lyo or placebo will be administered daily every 24 hrs for 6 days (D0 – D5). The first dose will be given after successful surgery at the point when the patient arrives to the ICU.

No dose modifications or short interruptions of study treatment are allowed.

Retreatment with a second course of study medication is not permitted.

Number of patients

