8.5 Evaluation of efficacy

8.5.1 *Evaluation of primary efficacy endpoint*

The primary endpoint of the study will be:

- All-cause mortality at D30

To be eligible for efficacy analysis each patient must receive at least two doses of the study medication with an effect time of 12 hours after second dose. This means that a death within 36 hours from the first dose of study treatment leads to exclusion from efficacy analysis. This derives from the fact that based on the prior clinical phase I/II studies with interferon beta-1a, its effect on the expression of CD73 and production of adenosine will require 12 to 24 hours from administration of the drug. Thus, therapeutic levels will not be reached until 12 hours from the second dose, i.e. 36 hours from the first dose. Measuring efficacy against multi-organ failure prior to this point is misleading because therapeutic levels have not yet been reached.

The efficacy analyses will be conducted using logistic regression model for the observed mortality rates in the two treatment groups. Stratification factors used in the randomisation will be included in the model. Primary result will be presented as an adjusted odds ratio and a 95% CI for the adjusted odds ratio. Also, a 95% confidence interval (CI) for the difference in the observed mortality rates will be calculated. A two-sided significance level of 0.05 will be used for all analyses.

There will additionally be an evaluation of the homogeneity of the treatment effect by investigating treatment by centre and treatment by baseline factor interactions in the logistic model. Data for the primary efficacy endpoint will also be presented for key, pre-defined subgroups of patients together with 95% CIs for the difference in those rates to supplement the investigation of homogeneity. Mortality at D30 will be illustrated also using survival function and Kaplan-Meier curves including log-rank test as an exploratory analysis.

8.5.2 *Evaluation of secondary efficacy endpoints*

By way of further confirmatory measures of efficacy, the following endpoints will be analysed:

- Time and reason/diagnosis of death up to D90 (3 months)
- Number of VFDs up to D30
- Number of days receiving hemodialysis at D30 and D90
- Number of ICU free days up to D30
- Organ failure free days up to D30
- Neutralizing antibodies IFN beta (NAbs) in whole blood samples up to D30
- Number of days in hospital up to D30 and D90 (length of stay in another health care facility)

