Patients will receive 10 µg FP-1201-lyo or placebo intravenously as a bolus injection once every 24 hours. The maximum duration of treatment will be 6 days. Treatment may be discontinued before 6 days if the patient's condition improves beyond the need for ICU treatment and if, in the opinion of the Investigator, the patient would likely not benefit from continuation of treatment.

With an estimated screening failure rate of approximately 15%, a maximum of 180 patients were planned to be consented and entered into the study in order to randomise and initiate treatment of 152 patients.

Study was discontinued after an Interim analysis.

5 Study variables

The following variables will be evaluated

The demographic and baseline variables

Gender, age at entry, race, weight (predicted or actual), height, medical history, concomitant medications/therapies, major surgical outcomes affecting patient and pregnancy test (females of child bearing potential, and peri procedural information (duration of the surgical procedure for RAAA, total clamping time, total bleeding volume, total volume substitution, total blood substitution, total red blood cells substitution, total platelets substitution, total crystalloids substitution and total diuresis volume during procedure and recycling of blood during surgery (yes/no)).

The primary efficacy outcome variable

- All-cause mortality at D30

The secondary efficacy outcome variables

- All-cause mortality at D90 (3 months)
- Number of ventilator free days (VFDs) at D30
- Number of days receiving haemodialysis at D30 and D90
- Number of organ failure free days up to D30 by means of the SOFA score
- Prevalence of abdominal compartment syndrome, i.e. intra-abdominal pressure (IAP) between treatment groups
- Neutralizing antibodies against IFN beta (NAbs) in whole blood samples up to D30

- Disability on D90 measured by modified ranking scale (mRS)

Safety variables

Adverse events, vital signs (body temperature, blood pressure, heart rate), physical examination and clinical laboratory parameters (biochemistry and haematology).

Pharmacodynamic (PD) and tentative disease specific marker variables

- MxA (protein) concentration in whole blood samples from baseline up to D13
- CD73 concentration in serum samples from baseline up to D6
- Potential Inflammatory Markers (IL-6 and HGF) in serum samples from baseline up to D13

Pharmacoeconomic variables

- Length of ICU stay, in terms of ICU free days at D30

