12.2 Secondary efficacy variables

The following secondary endpoints will be analysed:

- Time and reason/diagnosis of death up to D90 (3 months)
- Number of VFDs up to D30
- Number of days receiving hemodialysis at D30*
- Number of ICU free days up to D30*
- Organ failure free days up to D30
- Number of days in hospital up to D30 (length of stay in another health care facility)*
- Prevalence of abdominal compartment syndrome, i.e. intra-abdominal pressure (IAP) value differences between study groups
- Disability on D90 measured by modified ranking scale (mRS)
- Neutralizing (and anti-drug) antibodies IFN beta (ADAs and NAbs) in whole blood samples up to D30

*ICU free days and number of days in hospital, length of stay in another health care facility and number of days receiving hemodialysis at D90 summarized in pharmacoeconomic tables

All-cause mortality at D90 (3 months) will be compared using Cox regression model including stratification factors (if feasible). Estimated hazard ratios will be presented with associated 95% CIs and log-rank p-values for the FAS-E. Also, similar logistic regression as for the primary endpoint (D30 mortality) will be done.

For endpoints number of VFDs, number of ICU free days, organ failure-free days, number of days on hemodialysis, number of days in hospital, length of stay in another health care facility and IAP values, data will be summarised in terms of the mean, median, minimum and maximum, and the treatment groups will be compared using the Mann-Whitney U-test. Descriptive tables of IAP grade by timepoint will be presented using counts and percentages. Number of days on hemodialysis, number of days in hospital, length of stay in another health care facility and IAP value analyses will be performed for all patients and excluding deaths separately.

Complete data on organ failure free days may be unavailable due to SOFA scores not being assessed after ICU treatment. To account for this, the number of organ failure free days will be analysed by expressing these as a proportion of the days on which SOFA scores are available.

Disability measured with mRS will be summarized descriptively and the treatment groups will be compared using the Cochran-Mantel-Haenszel test for trend.

ADAs and NABs in whole blood samples up to D30 will be summarized using descriptive statistics.

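### The post-interim SAP drops haemodialysis days at D90, a named secondary efficacy endpoint, under a pharmacoeconomic label, and section 15 does not declare it as a lost secondary efficacy endpoint

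*SAP*

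**What the plan says.** The protocol names haemodialysis days at both time points as secondary efficacy in the synopsis, in 3.2.1 and in 8.5.2, where the item to be analysed reads "Number of days receiving hemodialysis at D30 and D90". SAP section 5 keeps the endpoint under secondary efficacy: "Number of days receiving haemodialysis at D30 and D90".

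The analysis list in SAP 12.2 is shorter: "Number of days receiving hemodialysis at D30", marked with an asterisk. The footnote says that ICU, hospital and other-facility measures go elsewhere, together with "number of days receiving hemodialysis at D90 summarized in pharmacoeconomic tables". SAP 12.3.2 lists length of haemodialysis at D90 among the pharmacoeconomic endpoints and closes: "Due to early discontinuation of the study, these endpoints will not be analysed".

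SAP section 15 repeats that the endpoints of 12.3.2 will not be analysed because the study ended early. It calls them pharmacoeconomic and then concludes: "There are no other major deviations in the statistical analysis plan from the analyses planned in the study protocol".

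The protocol also gives the measure a second home. The synopsis and 3.2.3 list "Length of haemodialysis needed" (with a minor spelling difference in 3.2.3) under pharmacoeconomics, and 6.5 lists haemodialysis days to D30 and D90 there.

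**The concern.** A pre-specified secondary efficacy endpoint loses one of its two time points through a footnote in one section and a cancellation in another. Neither place says that secondary efficacy is affected. A reader who goes only to the deviations section would conclude that health-economic outputs were given up and nothing else of weight.

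The D90 time point carries clinical meaning that D30 cannot supply. Protocol 6.2.7 and 7.7 treat dialysis at D90 as permanent, and 7.7 notes that reversible renal failure after rupture has often cleared by three months. Laboratory summaries, creatinine included, stop at D30 (SAP 13.2), and treatment-emergent adverse events are not collected in mid-term follow-up (SAP 13.1). No other scheduled D90 variable is specific to the kidney. The protocol's introduction counts acute renal failure among the main causes of post-operative death.

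The current SAP version was written after the interim analysis. Its predecessor, dated 17.6.2019, concentrated on the primary analyses (SAP section 2). Choices about secondary endpoints made at that stage need a visible reason.

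**Working it through.** No figure in the plan needs recomputing. The check follows the endpoint through the documents and then tests the stated reason, the declaration and the timing.

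**1. Where the D90 count goes**

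| Place | Treatment of haemodialysis days at D90 |
|---|---|
| Protocol synopsis, 3.2.1, 8.5.2 | Secondary efficacy |
| Protocol 6.5 | Also pharmacoeconomic |
| SAP 5 | Secondary efficacy |
| SAP 8 and 12.3 | Pharmacoeconomic variables are to be analysed |
| SAP 12.2, list | Absent; D30 only |
| SAP 12.2, footnote | To be summarised in pharmacoeconomic tables |
| SAP 12.3.2 | Not analysed |
| SAP 15 | Not analysed, by cross-reference to 12.3.2 |
| SAP 19.3 | No D90 haemodialysis table and no pharmacoeconomic tables |
| SAP 19.4 | Listing 16.2.18 of haemodialysis days, no time limit stated |

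Sections 5, 8, 12.2 (footnote) and 12.3 point one way; 12.3.2, 15 and 19.3 point the other. The footnote refers to tables that the table plan does not contain. A programmer working from 12.2 and one working from 12.3.2 would deliver different outputs.

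**2. Size**

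SAP section 5 lists seven secondary efficacy variables: D90 mortality, ventilator-free days, haemodialysis days, organ-failure-free days, abdominal compartment syndrome, neutralising antibodies and D90 disability. One of the seven loses its D90 part. Tables 14.2.1.9.1 to 14.2.1.9.4 make four haemodialysis tables, all to D30; the number for D90 is zero.

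D90 days in hospital and in other facilities, which protocol 8.5.2 also places among the secondary endpoints, disappear by the same route. Tables 14.2.1.10.x and 14.2.1.11.x stop at D30.

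**3. Does early discontinuation explain it?**

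SAP section 2 says that the analyses will use the data gathered so far. D90 mortality keeps six tables (14.2.1.3.x, 14.2.1.4.x and 14.2.1.5.x, two each) and D90 disability keeps two (14.2.1.14.x). That is 6 + 2 = 8 tables at D90, against none for haemodialysis. Protocol 7.7 gathers need for dialysis at the same final follow-up as the disability score, and the flow charts in both documents mark a dialysis check at D90. If stopping early left enough D90 data for two endpoints, it does not alone account for dropping the third.

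**4. Is it declared?**

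In part. Section 15 names 12.3.2, and the list there includes D90 haemodialysis. The missing statement is that this item is also a secondary efficacy endpoint.

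**5. What is known about timing?**

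Protocol 5.4 planned to open the randomisation code for the interim, and SAP section 2 places this version after it. SAP section 8 says that the subject classification was still to be signed before database lock. Neither document says who saw interim results by arm, or what the SAP of 17.6.2019 said about this endpoint.

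**The case against.** The strongest reply is that nothing was hidden. Section 12.2 marks the move with an asterisk and a footnote, section 15 reports the cancellation, and the pharmacoeconomic label comes from the protocol itself (synopsis, 3.2.3 and 6.5). This stands against any claim that the loss was undeclared or that the label was invented to cover it. It does not remove the efficacy role, which the protocol gives in three places and SAP section 5 repeats.

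A second reply is that a count of days is harder to obtain than a single status. The D90 flow-chart entry is a check of whether the patient is on dialysis, daily assessments stop on transfer or discharge, and protocol 7.7 foresees refusal and loss to follow-up. Mortality and disability each need only one status at D90. This stands as a caution: the documents do not show that D90 day counts are complete. Protocol 6.2.7 nevertheless says the count will be assessed at D90, and the SAP does not give incomplete data as its reason. The argument about permanent renal failure also rests more on D90 status than on the count.

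Third, the practical loss is limited. D30 haemodialysis is still compared with and without deaths, a patient listing remains, and all secondary analyses are supportive and unadjusted, in a trial stopped after an interim on 35 evaluable patients. That is correct, and it limits the weight of the point.

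**Conclusion.** The point holds as a defect of specification and reporting. Haemodialysis days at D90 is a named secondary efficacy endpoint that the current SAP removes from analysis under a pharmacoeconomic label. The SAP contradicts itself on whether it will be summarised, and section 15 does not describe the loss as one of secondary efficacy. The size is one time point of one among seven secondary efficacy endpoints, plus D90 hospital and other-facility days lost in the same way. No primary or safety conclusion depends on it.

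This reading assumes that 12.3.2 overrides the footnote in 12.2; the table plan and section 15 both support that.

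A reader might infer that the endpoint was dropped silently after unblinding because of what the data showed. The documents do not support this. Section 15 declares the cancellation by cross-reference, and the timing evidence shows only that this version follows the interim, not that its authors saw results by arm. What remains is a risk of selective reporting, because the choice postdates the interim and the stated reason does not separate this endpoint from the D90 endpoints that were kept. A reader might also infer that complete D90 dialysis data exist for every patient; the documents do not show that either.

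**What to change.** In SAP 12.2, restore haemodialysis days to D90, analysed on the available data with the method already stated for D30: summary statistics and the Mann-Whitney U-test, for all patients and excluding deaths. Report how many patients contribute a D90 count. Add tables beside 14.2.1.9.x for FAS-E and PPS (2 analysis sets × 2 treatments of deaths = 4 tables), and take the item out of the 12.3.2 cancellation.

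If it is still to be dropped, list it in section 15 as a dropped secondary efficacy endpoint. Give a reason specific to it, such as the completeness of day counts after D30 if that is the obstacle, and amend the closing statement on other deviations.

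In either case, reconcile SAP sections 5, 8, 12.2, 12.3 and 12.3.2, and treat D90 days in hospital and in other facilities the same way. Mirroring their D30 tables would add up to eight more (4 + 4).

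Haemodialysis status at D90 by arm would be a useful descriptive summary, but neither document lists it as an endpoint, so it should be optional and labelled as not pre-specified.

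The cost is a handful of tables from data the protocol already plans to collect, and a few lines of SAP text. No new data collection is needed.
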